## **7.2 Study Population**

### **7.2.1 Subject Distribution**

Description of the subject enrollment, dropout cases, completion of scheduled treatment, and premature discontinuation: number of subjects and percentage;

Distribution of subjects in each data set;

Distribution of subjects with evaluable efficacy;

Listing of dropout and premature discontinuation by subject: status of drug administration, reasons for trial termination, etc.

### **7.2.2 Protocol violations and deviations**

Summarize and describe the protocol violations and deviations. See Appendix 1 for the classification of protocol violations.

### **7.2.3 Analysis of subject characteristics of two groups**

Age: Describe using mean, standard deviation, maximum, minimum, and median.

Gender: Calculate the percentage.

Height and weight: Describe using mean, standard deviation, maximum, minimum, and median.

Tumor history: The course of disease is described using mean, standard deviation, maximum, minimum, and median. The percentages for pathological grade, clinical stage, presence of extrahepatic metastasis, presence of vascular invasion, alpha-fetoprotein (AFP < 400 µg/L, ≥ 400 µg/L; AFP < 200 µg/L, ≥ 200 µg/L), and cause of liver cancer (HBV infection: positive for either HbsAg or HbeAg; HCV infection: positive) are calculated.

Target lesion and non-target lesion at baseline: The sum of diameters of target lesion is described using mean, standard deviation, maximum, minimum, and median. The percentages for target lesion, location of target lesion, non-target lesion, and location of non-target lesion are calculated.

The percentages for history of primary lesion surgery, local ablation therapy, interventional procedure, radiotherapy, systemic treatment, past medical history, and drug allergy are calculated. Among them, the history of primary lesion surgery and past medical history are coded by the system organ class (SOC) and preferred term (PT) of the ICH Medical Dictionary for Regulatory Activities (MedDRA 21.0, Chinese version). The percentages for number of local ablation therapies and number of past interventional procedures are calculated.

The percentages for baseline ECOG PS, Child-Pugh classification of liver function, Barcelona clinic liver cancer (BCLC) staging, and hepatitis B and hepatitis C markers (including HbsAg, HbsAb, HbeAg, HbeAb, HbcAb, and HCV) are calculated.

Baseline vital signs (body temperature, heart rate, respiratory rate, and blood pressure): describe using mean, standard deviation, maximum, minimum, and median. The baseline is defined as the closest recent non-missing measured value to date of drug administration taken.

Baseline physical examination of various systems: The percentages of normal, abnormal, and unchecked results are calculated.

Baseline quality of life (QLQ-C30) scores and EORTC QLQ-HCC18 scores in various dimensions: describe using mean, standard deviation, maximum, minimum, and median.

## **7.3 Efficacy Evaluation**

### **7.3.1 Analysis of primary efficacy endpoint**

The primary efficacy endpoint for this study is OS. The OS analysis is performed based on FAS and PPS when at least 312 deaths are collected in this study (≥ 80% of patients died), of which FAS is the primary analysis set.

The survival functions of the apatinib group and placebo group are estimated by the Kaplan-Meier method, and the survival curve is plotted. The survival functions of the two groups are compared using the log-rank test with and without considering the stratification factors for randomization. In this study, the stratified log-rank test considering the stratification factors in randomization system is the primary test. In addition, under the assumption of proportional hazards, the Cox proportional hazards models with and without stratification factors are used to estimate the hazard ratio (HR) and calculate the corresponding 95% CI. In addition, the Cox proportional hazard model including other baseline factors may also be considered to estimate the HR between the two groups and calculate its 95% CI.

For the sensitivity analysis of OS, see Section 7.6.2.

### 7.3.2 Analysis of secondary efficacy endpoints

- Secondary efficacy endpoints of PFS and TTP are summarized using descriptive statistics based on FAS and PPS according to the above general principles and analyzed using similar methods as those for primary efficacy endpoint.
- Based on FAS and PPS, the 3-, 6-, and 12-month PFS rates, the Kaplan-Meier method was used to estimate rates and corresponding 95% CIs of the two groups are calculated using the log-log transformation according to the normal approximation with back transformation to CIs on the untransformed scale.
- The secondary efficacy endpoint DOR, including the investigator assessed results as per RECIST v1.1, is analyzed based on FAS and PPS. DoR will only be assessed in subjects whose BoR is PR or CR. The end date of tumor response must be consistent with the PD date of PFS or the date of death, and the Kaplan-Meier product-limit method will be used to calculate the median survival time of each treatment group and estimate the corresponding 95% CIs. The analysis is carried out using methods similar to those for the primary efficacy endpoint.
- Based on FAS, PPS, and evaluable patients, the ORR and DCR in the two groups are calculated and their 95% CIs are calculated using the Clopper-Pearson method. The difference of rates between groups are calculated and its 95% CIs are calculated using the Wald (normal approximation) method. The P values are calculated by the stratified Cochran–Mantel–Haenszel (CMH) (primary analysis) and the unstratified Pearson chi-square tests. Confirmed and unconfirmed CR/PR are analyzed, respectively.
- Based on FAS, PPS, and evaluable patients, the percentage of patients with SD for  $\geq 6$  weeks are calculated, and their 95% CIs are calculated using the Clopper-Pearson method. The difference between groups and its 95% CI are calculated using the Wald (normal approximation) method. The P values are calculated by the stratified CMH and the unstratified Pearson chi-square tests.

- Based on FAS and PPS, the 6- and 12-month OS rates, the Kaplan-Meier method is used to estimate rates and corresponding 95% CIs of the two groups are calculated using the log-log transformation according to the normal approximation with back transformation to CIs on the untransformed scale.
- Based on the FAS, the changes of the total quality of life scores from baseline between the two groups for each time point are compared by analysis of variance model (ANOVA). The changes from baseline in global health status, total quality of life score, and score of EORTC QLQ-HCC18 at each scale for each time point are compared by Wilcoxon rank-sum test between groups.

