1.5.7 Results of phase II clinical trial of apatinib in patients with HCC

A randomized, open-label, multi-center phase II clinical trial evaluating apatinib mesylate tablets in advanced HCC was initiated in Jul. 2010 by the 81st Hospital of the Chinese People's Liberation Army and other sites.

The trial involved two treatment groups: 850 mg and 750 mg groups. Primary endpoint: TTP; secondary endpoints: OS, ORR, DCR, AFP, QoL, and safety.

Simon's two-stage design for the clinical study of anti-tumor drugs is used. Sample size is determined based on disease control rate (DCR). It was assumed that patients receiving the best supportive care for this indication could achieve DCR of 30%. Patients in the apatinib group achieved DCR of 50%, indicating that apatinib is superior to the best supportive care in terms of DCR. Based on the optimal design criteria, with $\alpha = 0.05$ and $\beta = 0.2$, and using

NCSS & PASS, 15 patients were enrolled in each group in the first stage. If 5 patients reach DCR, the sample size would be expanded to 46 patients. If 15 of the 46 patients reach DCR, subsequent studies could be carried out at this dose. Taking dropout factors into consideration, a total of 36 subjects were enrolled in the first stage, and sample size was expanded to 117 in the second stage, i.e., 81 subjects were enrolled (including 51 in the 850 mg group and 30 in the 750 mg group).

As of Jun. 2013, the results are as follows:

The phase II clinical trial of apatinib mesylate tablet in patients with advanced HCC had an actual enrollment of 121 subjects, including 70 in the 850 mg group and 51 in the 750 mg group.

Efficacy results showed that in the FAS (ITT population), mTTP values in the 850 mg and 750 mg groups were 4.2 and 3.3 months, and mOS values were 9.7 and 9.8 months, respectively. ORRs were 8.6% and 0.0%, and DCRs were 48.6% and 37.3%, respectively.

Table 4. Inter-group comparison of efficacy results (FAS)

Group	mTTP (month)	mOS (month)	ORR (%)	DCR (%)
850 mg	4.2	9.7	8.6	48.6
750 mg	3.3	9.8	0.0	37.3

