## 3.2 Secondary Efficacy Endpoints

- Progression free survival (PFS): the time from the date of randomization to onset of progressive disease (PD) (as per RECIST 1.1) or death, whichever occurs first;
- 3-, 6-, and 12-month PFS rates;
- Time to progression (TTP): the time from the date of randomization to any documentation of radiologic progression (as per RECIST 1.1);
- Duration of response (DOR): the time from the first recording of tumor response to the first recording of objective tumor progression or death of any cause;
- Objective response rate (ORR): the proportion of subjects with confirmed complete response (CR) and partial response (PR) when the objective response is assessed as per RECIST 1.1;

- The proportion of subjects with stable disease (SD) for  $\geq 6$  weeks;
- Disease control rate (DCR): the proportion of subjects with confirmed CR, PR, and SD (for  $\geq 6$  weeks);
- 6- and 12-month survival rates;
- Quality of life score: EORTC QLQ-C30 and HCC18.

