#### **7.1.1 Significance level**

For group comparisons, all hypothesis tests are performed using two-sided tests with an  $\alpha = 0.05$ . If  $P$  is  $\leq 0.05$ , the difference of the test is considered to be statistically significant. A 95% confidence interval is used in this study.

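### The SAP's wording for duration of response most naturally calls for a log-rank test and hazard ratio among responders only, which is not a randomized comparison and would carry little information

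*SAP*

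**What the plan says.** SAP 3.2 defines DOR as "the time from the first recording of tumor response to the first recording of objective tumor progression or death of any cause". It is listed there as a secondary efficacy endpoint. It does not appear among the secondary endpoints in Protocol 2.3 or 10.2, so the SAP is its only specification.

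SAP 7.3.2 names the full analysis set (FAS) and per-protocol set for DOR, then adds "DoR will only be assessed in subjects whose BoR is PR or CR". It asks for a Kaplan-Meier median and 95% CI in each arm, and closes with "The analysis is carried out using methods similar to those for the primary efficacy endpoint".

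SAP 7.3.1 sets out those primary-endpoint methods: Kaplan-Meier curves; log-rank tests between arms, where "the stratified log-rank test considering the stratification factors in randomization system is the primary test"; and Cox models, stratified and unstratified, giving an HR with 95% CI.

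SAP 7.1.1 applies a two-sided 0.05 level to all group comparisons. If P is at or below 0.05, "the difference of the test is considered to be statistically significant". SAP 7.4.1 says that P values for adverse-event incidences are for clinical reference only. DOR has no such qualification.

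**The concern.** Randomization balances everyone assigned to each arm. It does not balance those who later respond, because response is an outcome that the drug may change. Apatinib responders and placebo responders are therefore differently selected groups, and each responder's clock starts at response rather than at randomization. A log-rank P value or HR between them mixes any effect on duration with the difference in who responds. If apatinib adds responders whose responses are short, the comparison can count against the drug although it shortened nobody's response. If the added responses are long, the comparison can flatter it.

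At stake is one secondary result that could be reported as significant, in either direction, when it does not estimate a treatment effect. Naming the FAS as the analysis set does not repair this, since the restriction to responders leaves only a small part of it.

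**Working it through.** **1. Does the text call for a between-arm test?** The DOR bullet has already specified Kaplan-Meier medians and CIs when it reaches the sentence on similar methods. If that sentence adds anything of substance, it adds the log-rank test and Cox HR of SAP 7.3.1. The PFS/TTP bullet in the same section uses nearly the same phrase, and a between-arm comparison is plainly meant there. This is the most natural reading, but it is an inference.

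**2. Can selection alone create a difference?** Illustration with assumed values: 2% of patients respond in either arm, with a median DOR of 6 months in both; a further 6.6% respond only on apatinib. Placebo responders then have a median of 6 months. Among apatinib responders the first type makes up 2/8.6 = 23.3% and the second 76.7%. With exponential durations, the apatinib median t solves

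0.233 × 2^(−t/6) + 0.767 × 2^(−t/m) = 0.5,

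where m is the median of the apatinib-only responders.
- m = 3 months: t = 3.5 months, against 6 on placebo.
- m = 12 months: t = 10.1 months, against 6 on placebo.

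In both cases nobody who would respond in either arm has a changed duration. A simulation of the m = 3 case (260 and 130 patients, no censoring, unstratified) gave a median one-step HR of about 1.40 against apatinib. With every median at 6 months the median one-step HR was 0.84, and the nominal 5% test rejected in about 11% of the runs where a comparison was possible. That second result is a small-sample failure of the test, separate from the selection problem.

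**3. How many responders?** The documents give no expected responder count or power for DOR, so there is no planned figure to reproduce. Inputs: 390 patients at 2:1 (Protocol 4.1), hence 260 and 130; and phase II results in HCC (Protocol 1.5.7) for 850 mg (70 patients) and 750 mg (51 patients), where "ORRs were 8.6% and 0.0%, and DCRs were 48.6% and 37.3%, respectively".

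| Basis | ORR | Apatinib responders of 260 |
|---|---|---|
| 750 mg, 0/51 | 0%; exact 95% upper limit 1 − 0.025^(1/51) = 7.0% | 0 to 0.070 × 260 = 18 |
| 850 mg, 6/70 | 8.6% | 22 (exact 95% limits 8 to 46) |
| Pooled, 6/121 | 5.0% | 13 (exact 95% limits 5 to 27) |

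The trial's starting dose is 750 mg. Neither document gives a placebo ORR for HCC. Assuming 0% to 2%, the expected number is 0 to 0.02 × 130 = 2.6; at an extreme 5% it is 6.5. The chance of no placebo responder, (1 − p)^130, is 100% at p = 0%, 27% at 1% and 7% at 2%. With none, there is nothing to compare.

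**4. How much information?** Best case: every responder has an event. Schoenfeld power is Φ(√(e·a·(1 − a)) × |ln HR| − 1.96), where e is the number of events and a the apatinib share of them. For 22 versus 3 responders, e = 25, a = 0.88 and e·a·(1 − a) = 2.64.
- HR 6/8.5 = 0.706 (the OS design value): Φ(1.625 × 0.348 − 1.96) = 8%.
- HR 0.5: Φ(1.625 × 0.693 − 1.96) = 20%.

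**5. The stratified version.** Three binary factors (SAP 2.5) make 2 × 2 × 2 = 8 strata. A stratum without responders in both arms contributes nothing to the test, so three placebo responders can inform at most three strata.

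**The case against.** The strongest reply is that the SAP never says DOR will be compared between arms. Its explicit output is a median and CI for each group, the word similar is loose, Kaplan-Meier estimation is itself one of the primary-endpoint methods, and the only formal hypothesis (SAP 7.1.2) concerns OS. This stands to the extent that the test is inferred rather than stated. It does not remove the ambiguity, because the parallel PFS/TTP wording points to a test and nothing points away from one.

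Four further points stand in full:
- Restricting DOR to responders is not an error. It follows from the definition, and the fix keeps it.
- A reader might take 18 as the most responders that apatinib could produce. It is a confidence limit from 51 patients. The 850 mg rate gives about 22, and Protocol 1.5.7 calls the two doses comparable in efficacy.
- A reader might infer that the analysis cannot be estimated because of the 8 strata. Sparse strata affect only the stratified version, and SAP 7.3.1 also specifies unstratified analyses. With no placebo responders neither version works, but the responder counts would show that.
- Much of the remedy is already planned: medians by arm, and ORR in the FAS with a stratified CMH test as primary. The FAS (SAP 6.1) is randomized patients with at least one dose, analysed as randomized.

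**Conclusion.** The point holds as a minor one. On its most natural reading the SAP would produce a P value and HR for DOR that are not a treatment effect, with no caveat against calling them significant. That conclusion rests only on response being a post-randomization outcome that treatment can affect; it needs none of the numbers.

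The numbers show that the comparison would also be weak: roughly 0 to 18 apatinib responders on the 750 mg data or about 22 at the 850 mg rate, against 0 to 3 on placebo. They rest on the phase II rates carrying over and on an assumed placebo ORR of 0% to 2%. The simulated HR and rejection rate rest on assumed response rates and durations and are illustrations only.

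A reader might go further and infer that the trial's main conclusion is at risk. The documents do not support that. Protocol 4.2 judges superiority on OS alone, and the OS sample size, its 312 deaths and its alpha do not depend on DOR.

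**What to change.** In the DOR bullet of SAP 7.3.2, delete the sentence on methods similar to the primary endpoint, or state that for DOR it covers Kaplan-Meier estimation only. Report by arm the number of responders, the Kaplan-Meier median and its 95% CI, labelled descriptive, with no between-arm P value or HR. Add that any between-arm claim about response rests on the ORR analysis already planned in the FAS.

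The cost is one sentence of SAP wording and slightly less analysis. No sample size, event count or alpha changes. If description was all that was intended, the same sentence settles it.

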9 STUDY PROCEDURES

9.1 Screening Period (from signing informed consent form to obtaining random numbers)

Subjects must sign the informed consent form before undergoing any screening procedures.

Unless otherwise stated, the following screening procedures should be completed within 21 days prior to randomization.

- Patients sign the informed consent form.
- Collection of medical history, including past treatment history, current medical history, drug allergies, and concurrent diseases.
- Physical examination, height, weight, and vital signs (body temperature, blood pressure, heart rate, and respiratory rate).
- Chest x-ray, not required if the subject have undergone chest CT.
- CT or MRI of the chest, abdomen, pelvis and other relevant lesions.
- Brain CT/MRI, required for clinically suspected metastases to the central nervous system only.
- Bone scan, required for clinically suspected bone metastasis only.
- Test of hepatitis B and hepatitis C markers, and HBV DNA.
- Test of serum AFP.

The following information should be collected within 7 days before randomization:

- ECOG PS.
- Hematology, urinalysis, and routine stool test.
- Hepatic and renal function (total bilirubin, direct bilirubin, indirect bilirubin, ALT, AST, AKP, r-GT, LDH, total protein, albumin, blood urea nitrogen, creatinine, uric acid).
- Electrolytes (potassium, sodium, chlorine, calcium, phosphorus).
- Coagulation function (PT or INR).
- Pregnancy test (serum or urine, only for women of childbearing potential).
- Echocardiography (mainly to observe LVEF).
- 12-Lead ECG (the QTc interval must be indicated), for 3 times with about 5 minutes apart.
- Quality of life score (EORTC QLQ-C30 and HCC18).
- Randomization should be carried out after all screening evaluations are completed.

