## 2.5 Randomization Method

The randomization method used in this trial is as follows: Subjects are randomized to two groups in a 2:1 ratio to receive apatinib or placebo treatment.

The subjects are allocated by central randomization and enrolled competitively at all sites. The central randomization system provided by the Department of Biostatistics of Nanjing Medical University will be used for central randomization. After all eligible subjects are screened by study personnel at each study site participating in this trial and confirmed by the investigator of each site, their screening information will be entered into the randomization system to generate the randomization numbers and drug numbers. Corresponding study drugs will be dispensed based on the drug numbers. Subjects must begin the assigned study treatment within 48 h after randomization.

Stratification factors for randomization include:

- ECOG PS: 0 or 1
- Treatment with sorafenib: yes or no
- Presence of vascular invasion and/or extrahepatic metastasis: yes or no

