## 7.4 Safety Evaluation

### 7.4.1 Adverse events

AEs are encoded according to the current MedDRA 21.0 and then processed in statistical analysis.

The incidences of AEs, treatment-related adverse events (TRAEs), AEs leading to drug interruption, dose reduction, and drug discontinuation, and SAEs are summarized. If multiple AEs occurred in the same subject, the number of subject is counted as one when calculating the incidence; if a subject experiences multiple times of a same AE, the number of subject is counted as one when calculating the incidence of the AE.

AEs are summarized in the frequency table based on SOC and PT. The incidence is calculated based on SOC and symptom/sign (the number of cases is counted as number of subjects who have experienced at least one AE).

Severity of AEs and treatment-related adverse events: If a subject experiences multiple times of the same AE, the most severe one will be used in the analysis of the severity of the AE.

A list of cases of AEs and SAEs is provided.

The median time to the onset of the first event is calculated for the adverse events of special interest (AESIs). AESIs include hypertension, proteinuria, hand-and-foot syndrome, hemorrhage, electrocardiogram QT prolonged, and white blood cell count decreased. The specific classification definitions are shown in Appendix 2.

Time to the onset of first event (days) = onset date of first event – date of the first dose + 1

In addition, for the comparisons of the incidences of AEs between the treatment group and the control group, the Fisher's exact method may be used to calculate the P value, which is only used for clinical reference, rather than the deduction of statistical significance.

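### Quality-of-life change is compared visit by visit with no baseline covariate and no lead visit or test; adjusting for the baseline score already collected is a cheap, optional precision gain

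*SAP*

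**What the plan says.** SAP 3.2 lists "Quality of life score: EORTC QLQ-C30 and HCC18" as the last secondary efficacy endpoint. SAP 7.3.2 sets out two sets of comparisons in the FAS:

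- Changes from baseline in the total quality of life score "for each time point are compared by analysis of variance model (ANOVA").
- A second set covers changes in global health status and two further kinds of score: "total quality of life score, and score of EORTC QLQ-HCC18 at each scale for each time point are compared by Wilcoxon rank-sum test".

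The total score therefore has two tests at each visit. Global health status, if it is a different score, has the Wilcoxon test only. Protocol 12.3 is no more specific: it allows ANOVA or a rank sum test for changes.

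Visits come from Protocol 10.2 and note h of the Schedule of Activities: baseline, end of Cycles 2 and 3, then every two cycles.

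The baseline score is available. Protocol 9.1 collects both questionnaires within 7 days before randomisation, and SAP 7.2.3 summarises "Baseline quality of life (QLQ-C30) scores and EORTC QLQ-HCC18 scores in various dimensions". The three randomisation factors (ECOG PS, prior sorafenib, vascular invasion and/or extrahepatic metastasis) are in SAP 2.5.

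On interpretation, SAP 7.1.1 says that when P is 0.05 or less "the difference of the test is considered to be statistically significant". For adverse events, SAP 7.4.1 marks the P value as one "which is only used for clinical reference, rather than the deduction of statistical significance". The quality-of-life bullet carries no such statement.

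**The concern.** A change score subtracts the baseline value with a fixed weight of one. Unless the regression of follow-up on baseline happens to have slope one, part of the baseline variation stays in the comparison as noise. ANCOVA estimates the weight from the data and removes that noise. Everything it needs is already collected.

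The second issue is clarity. The SAP marks the stratified log-rank test as primary for OS (7.3.1) and the stratified CMH test as the primary analysis for ORR and DCR (7.3.2). For quality of life it names no lead score, visit or test. If ANOVA and Wilcoxon disagree, or one visit differs from the next, the plan does not say which result answers the question.

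At stake are the width of the quality-of-life intervals and the readability of that section of the report. The primary conclusion is not at stake.

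**Working it through.** **Plan's own figure.** There is none to reproduce. The documents give no SD, correlation, target difference or power for quality of life. The only derived sample size (331) is for OS and does not bear on this point.

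**Inputs.** From the documents: change is follow-up minus baseline (SAP 7.1.3); allocation is 2:1 and planned enrolment 390 (SAP 2.4, 2.5), so about 260 v 130. Assumed: the baseline-to-follow-up correlation ρ (0.3 to 0.9), the ratio k of follow-up SD to baseline SD (0.8 to 1.25), and the numbers still assessed.

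**Step 1: large samples.** With the baseline SD set to 1, the per-patient variances are:

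- change score: 1 + k² − 2ρk
- ANCOVA on baseline: k²(1 − ρ²)

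Their ratio is k²(1 − ρ²) / (1 + k² − 2ρk). At k = 1 this is (1 + ρ)/2.

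| ρ | ratio at k = 1 | variance reduction |
|---|---|---|
| 0.3 | 0.65 | 35% |
| 0.5 | 0.75 | 25% |
| 0.7 | 0.85 | 15% |
| 0.9 | 0.95 | 5% |

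Over k from 0.8 to 1.25 the extremes are:

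- k = 0.8, ρ = 0.3: 0.64 × 0.91 / (1.64 − 0.48) = 0.5824 / 1.16 = 0.50, a 50% reduction.
- k = 1.25, ρ = 0.8: 1.5625 × 0.36 / (2.5625 − 2.00) = 0.5625 / 0.5625 = 1.00, no gain.

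Simulation at 2:1 and k = 1 agrees with the formula: 0.65 to 0.67, 0.74 to 0.76 and 0.84 to 0.87 at ρ = 0.3, 0.5 and 0.7.

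**Step 2: what this means for power.** Take an assumed difference of 0.3 SD of a single score. Power is Φ{0.3 / (s√(1/n₁ + 1/n₀)) − 1.96}, with s = √(2(1 − ρ)) for change and √(1 − ρ²) for ANCOVA.

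| ρ | 260 v 130: change, ANCOVA | 120 v 60: change, ANCOVA |
|---|---|---|
| 0.3 | 65.6%, 83.3% | 36.1%, 51.2% |
| 0.5 | 79.8%, 89.7% | 47.5%, 59.1% |
| 0.7 | 95.0%, 97.4% | 68.8%, 75.7% |

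These rows compare ANCOVA with ANOVA on change. Global health status is planned by Wilcoxon, so that comparison was simulated. The assumptions were 180 v 70 patients, SD 20, an 8-point difference and k = 1. Power was 63%, 77% and 93% for Wilcoxon on change and 84%, 89% and 97% for ANCOVA at ρ = 0.3, 0.5 and 0.7. At k = 1.25 the gap narrows to 49% v 64% at ρ = 0.3 and 83% v 86% at ρ = 0.7.

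**Step 3: few patients.** Estimating the baseline slope costs something. For normal data and one covariate, the ANCOVA variance is inflated on average by 1 + 1/(N − 4). At an assumed 20 v 8, N = 28 and the factor is 25/24 = 1.042.

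- k = 1: 0.65 × 1.042 = 0.68 to 0.95 × 1.042 = 0.99.
- k from 0.8 to 1.25: 0.502 × 1.042 = 0.52 to 1.00 × 1.042 = 1.04. Simulated upper ends were 1.03 to 1.04.

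Adjustment can therefore lose about 3% to 4% in the least favourable case. Adding three factors with no prognostic value at the same size raised the simulated ratio to as much as 1.17, which is why the fix uses the baseline score alone away from the lead visit.

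**The case against.** ANOVA or rank-sum on change is a valid analysis, and Protocol 12.3 specifies it. Quality of life is the last-listed secondary endpoint and was never powered. The gain rests wholly on a correlation that the documents do not give; it shrinks as ρ rises and can vanish. A repeated-measures model would be a reasonable alternative to per-visit ANCOVA. All of this stands, and it is why the point is an optional improvement and not an error.

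Three stronger readings are tempting, and the documents do not support them.

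- *That the plan ignores baseline.* It does not: the change score subtracts it. What is missing is a fitted weight.
- *That the tests are invalid or the trial's error rate is inflated.* Each test keeps its 5% level, and the formal hypothesis in SAP 7.1.2 concerns OS alone. Six on-treatment visits to Cycle 11 (Cycles 2, 3, 5, 7, 9, 11) would give 1 − 0.95⁶ = 26.5% for at least one P of 0.05 or less if independent, and less for correlated visits. That only illustrates why a lead analysis helps. It is not the plan's error rate: it counts one test of one score, and the SAP sets no multiplicity control for any secondary endpoint.
- *That adjustment would repair assessments missing after progression or death.* It would not, and this point makes no claim about missing data.

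**Conclusion.** The point holds as an optional precision and clarity improvement to a secondary endpoint. SAP 7.3.2 names no baseline covariate, lead visit or lead test for quality of life, and the data for a better analysis are already on file.

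The variance reduction against ANOVA on change is 35% to 5% for assumed ρ of 0.3 to 0.9 with equal SDs, and 50% to 0% if the SD ratio runs from 0.8 to 1.25. At 20 v 8 patients the variance ratio is about 0.68 to 0.99 with equal SDs and 0.52 to 1.03 or 1.04 over the wider range. Correlation, SDs, effect size and numbers assessed are all assumptions; the direction of the large-sample result is not, because the ratio in Step 1 never exceeds 1.

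A reader might infer that the quality-of-life results would be unsound or that the OS conclusion is affected. Neither follows: the planned tests are valid and the OS analysis does not use these scores.

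**What to change.** Before database lock and unblinding, amend the quality-of-life bullet in SAP 7.3.2 along these lines:

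- **Lead analysis:** change from baseline in global health status (items 29 and 30, 0 to 100 score) at the end of Cycle 2 in the FAS. Use ANCOVA with the baseline score and the three randomisation factors, and report the adjusted difference with its 95% CI.
- **Other visits, and the HCC18 scales:** ANCOVA with the baseline score alone, as supportive analyses.
- **Wilcoxon rank-sum on change:** keep as supportive.
- **P values:** state that all quality-of-life P values other than the lead one are for reference only, as SAP 7.4.1 does for adverse events, and cross-refer to this in SAP 7.1.1.
- **Minor:** define the total quality of life score or delete it. Protocol Appendix 9 lists a combined global health status/quality of life scale but no total. If the two are the same score, say so.

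**Cost.** No new data and modest programming. The method departs from the ANOVA or rank sum test in Protocol 12.3, and the SAP should say so. The model uses 4 degrees of freedom at the lead visit (baseline score plus three two-level factors) and 1 elsewhere. At late visits with few patients there may be a slight loss of precision.
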